### *Secondary Outcomes*

- Lactate change between 0- and 12-hours after administration of study drug
- Lactate change between 0- and 36-hours after administration of study drug
- Shock-free days
  - Shock-free days measured as days alive and free of shock (<6 hours receiving a vasopressor) over the first 7 days after enrollment.

- Ventilator-free days
  - Ventilator-free days measured as days alive and free of invasive mechanical ventilation (<6 hours with an endotracheal tube) over the first 7 days after enrollment.
- Length of initial Intensive Care Unit (ICU) stay truncated at 28-days
  - Includes only the initial stay in the ICU and does not include ICU readmission
- Length of initial hospital stay truncated at 28-days
  - Includes only the initial hospital stay and does not include any readmissions
- Survival to hospital discharge
- Neurologic outcome at hospital discharge
  - As defined using the Modified Rankin Scale
- Biomarker measures (available at 0-hours and 24-hours)
  - Interleukin (IL)-1 $\beta$ , IL-6, IL-8, IL-10, and TNF- $\alpha$
  - Neuron specific enolase [NSE]
  - S100 calcium-binding protein B (S100B)
- Muscle weakness assessed using a modified Medical Research Council scale

A table of outcomes by treatment group will be included (see Appendix Table 3).

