## Statistical Analysis

### *General Principles*

All initial analyses will be performed in a modified intention-to-treat (modified ITT) population, defined as all randomly assigned subjects who received any study drug (rocuronium or the saline time marker). The primary analysis for the outcome of lactate at 24-hours will be repeated in the per-protocol population including only those patients who were alive at 24-hours and received either 24-hours of continuous rocuronium (if so assigned) compared to those who received usual care without any neuromuscular blockade medication after the time 0-hour point.

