### *Analysis of Secondary Outcomes*

The following outcomes will be summarized using mean  $\pm$  SD or median (IQR) and linear regression using the above described linear mixed model will be performed to assess the differences between treatment groups.

- ICU length of stay
- Hospital length of stay
- Time to shock reversal
- Time to liberation from mechanical ventilation
- Biomarker measures (regression controlled for baseline level of each biomarker)
- Muscle weakness score

The following outcomes will be summarized using frequencies and percentages and logistic regression will be performed to assess the differences between treatment groups.

- Neurologic outcome at hospital discharge
- Survival to hospital discharge

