## Appendix

### *Appendix Figure 1*

*Appendix Figure 2 - Change in Lactate over Time*

*Appendix Table 1 - Cohort Characteristics*

Variable	NMB	Usual Care
Demographics		
Age (Median, IQR)		
Sex (%Female)		
Race (%White)		

Past Medical History		
Congestive heart failure		
Atrial fibrillation		
Coronary artery disease		
Prior cardiac arrest		
Chronic pulmonary disease		
Kidney disease		
Active malignancy		
Arrest Characteristics		
Location (%OHCA)		
Initial Rhythm (% Non-shockable)		
Estimated no-flow time (median, IQR)		
Estimated low-flow time (median, IQR)		
Arrest duration (minutes, median, IQR)		
Witnessed (%yes)		
Bystander CPR provided (%yes)		
Arrest etiology (%cardiac)		
Characteristics at Enrollment		
pH (median, IQR)		
pCO2 (median, IQR)		
pO2 (median, IQR)		
Shock stratification (% shock)		
STEMI present (%yes)		
Target temperature (median, IQR)		

Received any paralytic prior to enrollment (%yes)		
---	--	--

*Appendix Table 2 - Sedatives and Off-Protocol Paralytics*

Variable	NMB				Usual Care			
	0hr	12hr	24hr	36hr	0hr	12hr	24hr	36hr
Sedation and Analgesia (% receiving)								
Propofol								
Midazolam								
Lorazepam								
Dexmedetomidine								
Fentanyl								
Paralytic (% receiving)								
Bolus Rocuronium								
Continuous Rocuronium								
Bolus Cisatracurium								
Continuous Cisatracurium								

*Appendix Table 3 – Outcomes*

Variable	NMB	Usual Care	Effect estimate (95% confidence interval)
Lactate Level (mmol/L, median, IQR)			
0-hour			
12-hour			
24-hour			
36-hour			
Clinical Outcomes			
ICU LOS (days, median, IQR)			

Hospital LOS (days, median, IQR)			
Discharge CPC $\leq 2$ (%)			
Muscle Weakness Score (median, IQR)			
Hospital Survival (% survived)			

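### ICU and hospital length of stay are compared in all treated patients with no rule for death, so a survival difference between arms can appear as a difference in stay

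*SAP*

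**What the plan says.** The Protocol and SAP agree on this point. Under Secondary Outcomes the two measures are "Length of initial Intensive Care Unit (ICU) stay truncated at 28-days" and "Length of initial hospital stay truncated at 28-days". The only further rule for the ICU measure is: "Includes only the initial stay in the ICU and does not include ICU readmission". The hospital measure has the same kind of exclusion.

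The section on general principles places every initial analysis in the modified ITT set, meaning each randomised patient given rocuronium or the saline marker. That set is not limited to survivors.

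Analysis of Secondary Outcomes lists both stays among the outcomes for which "linear regression using the above described linear mixed model will be performed to assess the differences between treatment groups". Appendix Table 3 gives each a median and IQR per arm and a column for an effect estimate with a 95% confidence interval. It has no split by vital status.

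No section gives a survivor-only analysis, a fixed value for patients who die, or a competing-risk method. The same list of outcomes does take account of death elsewhere: "Ventilator-free days measured as days alive and free of invasive mechanical ventilation". Shock-free days are defined in the same way.

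**The concern.** A stay ends either because the patient recovers enough to leave or because the patient dies. With only a cap and a readmission rule, the number recorded does not tell the two apart. A patient who dies on day 2 scores 2; a survivor discharged on day 16 scores 16. A comparison across all treated patients therefore mixes survival with speed of recovery.

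The plan itself expects deaths inside the 28-day window. It chose the 24-hour lactate partly to avoid losing many patients to death at a later time point. Its background cites an association of neuromuscular blockade (NMB) with lower mortality and allows for better clinical outcomes. If survival did differ, the estimates and intervals for the two stays in Table 3 could not be read as effects on recovery, and a gain in survival could look like slower recovery.

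**Working it through.** **The plan's own figure.** The documents give no figure for length of stay. The only sample-size figure is for lactate: n per arm = 2 × (1.960 + 0.842)² × 3.2² / 2.0² ≈ 40.2, so 41 per arm and 82 in total. This agrees with the stated 80 (power at 40 per arm is 79.8%). It does not bear on the stays, except that it supplies 40 per arm for the illustration.

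**Formula.** Let p be the proportion surviving, S the mean stay of survivors and D the mean stay until death. If death closes the stay, the arm mean is p·S + (1 − p)·D. If NMB changes neither S nor D, the difference between arms is

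(p_NMB − p_usual) × (S − D).

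It is zero when survival is equal. It is positive when survival is better with NMB and deaths come before survivors' discharge (S > D). It is negative when survival is better and deaths come later.

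**Range.** With D from 3 to 8 days and S from 6 to 16 days (all assumed):

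- 10-point survival gain: from 0.10 × (6 − 8) = −0.2 to 0.10 × (16 − 3) = +1.3 days.
- 20-point survival gain: from 0.20 × (6 − 8) = −0.4 to 0.20 × (16 − 3) = +2.6 days.

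**Simulation.** Assumed inputs: 40 per arm; log-normal stays with log-SD 0.6; cap at 28 days; median 4 days to death; for survivors, median 8 ICU days plus median 8 ward days; no effect of treatment on stay within survivors or within deaths. Arms were compared by a two-sample t test, a simplification of the planned model without shock stratum and site. The mean stays after the cap are about 4.8 days (deaths), 9.4 days (survivors, ICU) and 18.0 days (survivors, hospital).

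The better-survival arm minus the other arm:

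| Mortality | Stay | Mean difference (days) | Longer in better arm | Significantly longer |
|---|---|---|---|---|
| 60% vs 60% | Hospital | 0 | 50% | 2–3% |
| 60% vs 60% | ICU | 0 | 50% | 2–3% |
| 60% vs 50% | Hospital | about +1.3 | 77% | 11% |
| 60% vs 50% | ICU | about +0.45 | about 65% | 6% |
| 60% vs 45% | Hospital | about +2.0 | 86% | 19% |
| 60% vs 45% | ICU | about +0.7 | 73% | 9% |

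The formula gives the same at 60% vs 45%: 0.15 × (18.0 − 4.8) = 2.0 and 0.15 × (9.4 − 4.8) = 0.7.

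**Later deaths.** With the median time to death raised from 4 to 8 days, equal to survivors' median ICU stay, the ICU difference at 60% vs 45% vanishes. The hospital difference falls to about +1.3 days and remains, because survivors also have ward days.

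**Alternative score.** Take days alive and out of the unit to day 28, with 0 for death. When stay within survivors is unchanged, the difference is (survival gain) × (28 − S). At 60% vs 45% this is 0.15 × (28 − 9.4) = +2.8 days out of ICU and 0.15 × (28 − 18.0) = +1.5 days out of hospital. Both favour the arm with better survival, and neither depends on when the deaths occur.

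**The case against.** The strongest reply is that this is a silence, not a choice. A reader might infer that the plan has decided to count early death as a good result. The documents do not say so. They are silent, and death closing the stay is only what the definition yields if nothing is added. That is correct, and it limits the point to a missing rule. It does not remove it, because the stated population and model need some value for each patient who dies.

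A reader might also infer that an arm that saves lives will show a longer stay, or that the estimate misleads whichever way mortality moves. That is not supported. The direction needs both a survival difference and deaths earlier than survivors' discharge, and the documents give no mortality rate or length of stay from which to check either. Even under the assumed inputs, most simulated trials show no significant difference in stay.

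The plan has partial safeguards. Survival to discharge is a separate outcome in the same table, and raw stay in all patients is a legitimate measure of resource use. Nowhere does the plan say that a longer stay will be read as harm. These points stand, but survival shown nearby does not turn the stay estimate into one of recovery. The shock-free and ventilator-free day counts help less than they might: Analysis of Secondary Outcomes lists time to shock reversal and time to liberation from ventilation instead, and Table 3 shows neither day count.

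Finally, a score with 0 for death partly restates mortality, and other methods exist, such as discharge alive with death as a competing event, or a worst-rank analysis. Both are fair. The score proposed here is preferred because it matches the approach the plan already takes for shock and ventilation.

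**Conclusion.** The point holds in conditional form. The two stays are compared in all treated patients with no rule for death, and on the literal reading a death counts as a short stay. The resulting estimate can then mislead about recovery whenever survival differs between arms and deaths tend to come before discharge.

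The hospital stay is more exposed than the ICU stay, since survivors' ward days widen the gap. Every mortality and stay input behind the sizes shown is an assumption, so the sizes illustrate the mechanism and do not predict this trial's result. The primary outcome and the survival analysis are unaffected; the matter is worth correcting for two secondary outcomes in a phase II trial.

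**What to change.** In Secondary Outcomes, Analysis of Secondary Outcomes and Appendix Table 3, make the between-arm comparison on days alive and out of ICU, and days alive and out of hospital, to day 28 from enrollment, with 0 for any patient dead by day 28. Keep the raw stays in Table 3 as description only, split into survivors and non-survivors, without a between-arm effect estimate.

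The cost is wording and table shells; the score mainly uses stay and survival data already planned. There are two downsides to state in the text. The score combines death and stay, so it must be read beside survival. Patients discharged alive before day 28 are assumed alive to day 28 unless later status is known. Because the documents describe conduct in the past tense and analysis in the future tense, record the date of the change and whether outcome data by arm had been seen.

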## Statistical Analysis

### *General Principles*

All initial analyses will be performed in a modified intention-to-treat (modified ITT) population, defined as all randomly assigned subjects who received any study drug (rocuronium or the saline time marker). The primary analysis for the outcome of lactate at 24-hours will be repeated in the per-protocol population including only those patients who were alive at 24-hours and received either 24-hours of continuous rocuronium (if so assigned) compared to those who received usual care without any neuromuscular blockade medication after the time 0-hour point.

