#### Statistical Analysis

#### General Principles

All initial analyses will be performed in a modified intention-to-treat (modified ITT) population, defined as all randomly assigned subjects who received any study drug (rocuronium or the saline time marker). The primary analysis for the outcome of lactate at 24-hours will be repeated in the per-protocol population including only those patients who were alive at 24-hours and received either 24-hours of continuous rocuronium (if so assigned) compared to those who received usual care without any neuromuscular blockade medication after the time 0-hour point.

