## Study Overview

### *Study Design and Setting*

This was a phase II, multi-center, randomized trial of continuous neuromuscular blockade using rocuronium vs. usual care in patients who had sustained return of spontaneous circulation (ROSC) but remained unresponsive after cardiac arrest. Enrolling sites were five urban tertiary care centers in the United States. The trial coordinating center gathered and analyzed the data, and vouches for the accuracy and completeness of the data and for the fidelity of the trial to the protocol. Written informed consent was obtained from the legally authorized representatives of all patients.

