### *Randomization and Intervention*

Patients were randomized to continuous NMB or usual care in blocks of four and in a 1:1 ratio. The randomization was stratified by study site and by the presence of shock, defined as the use of any vasopressor at the time of randomization. The random sequence was generated by an independent statistician who was not involved in the conduct of the study. The site-specific allocation sequences were maintained by the research pharmacies at each site for the duration of the study.

Patients in the continuous NMB arm received a rocuronium bolus of 1.0mg/kg followed by a continuous infusion of rocuronium for a total of 24-hours. The infusion of rocuronium was titrated to 1-2 out of 4 twitches on a train-of-four peripheral nerve stimulator. To minimize any difference in the time between randomization and receipt of the study drug between the two groups, patients in the usual care arm were administered a small volume of normal saline to mark the 0-hour time point. All patients undergoing TTM, including those who received continuous NMB, were deeply sedated per local site protocol. Use of the Columbia anti-shivering protocol was recommended to clinical teams, but adherence was not mandated.

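### Survival and other outcomes that need no dosing event are planned only in randomised patients who received study drug; these should be analysed in all randomised patients by assigned arm.

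*SAP*

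**What the plan says.** The Protocol, under General Principles, states: "All initial analyses will be performed in a modified intention-to-treat (modified ITT) population". The SAP section of the same name is identical and gives the definition: "all randomly assigned subjects who received any study drug (rocuronium or the saline time marker").

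The only other analysis set is narrower and applies to 24-hour lactate alone. That analysis "will be repeated in the per-protocol population including only those patients who were alive at 24-hours" and whose treatment followed the assigned regimen. Neither document specifies an analysis of everyone randomised, for any outcome.

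Three design statements bear on this:

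- **Comparator.** SAP, Study Design and Setting, describes a "randomized trial of continuous neuromuscular blockade using rocuronium vs. usual care". No blinding or masking is mentioned in either document as supplied.
- **What dosing means in each arm.** SAP, Randomization and Intervention: the active arm receives a bolus and then a 24-hour infusion "titrated to 1-2 out of 4 twitches on a train-of-four peripheral nerve stimulator", whereas "patients in the usual care arm were administered a small volume of normal saline to mark the 0-hour time point".
- **Custody of the allocation.** Same section: "The site-specific allocation sequences were maintained by the research pharmacies at each site". The text does not say who learns the assignment between randomisation and dosing.

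**The concern.** Receipt of study drug happens after randomisation. Restricting the analysis to dosed patients is safe when the decision to dose cannot depend on the assigned arm, and nothing in the documents secures that here. A team that knows the assignment may hold back a bolus and a long paralytic infusion in a patient whose condition is changing, yet have no reason to hold back a small volume of saline. Patients could then leave one arm for reasons linked to prognosis, and the groups compared would no longer be those that randomisation created.

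For lactate there is a reason to accept the restriction: time 0 is receipt of study drug, so the change score does not exist for an undosed patient. That reason does not carry over to survival to discharge, neurologic outcome at discharge or length of stay, none of which needs a dosing event. Shock-free and ventilator-free days are counted from enrollment, so they do not need one either. The plan gives no rationale for applying the restriction to these outcomes and no sensitivity analysis for it.

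**Working it through.** **The plan's own figure.** The sample size section gives a difference of 2.0 mmol/L, SD 3.2 mmol/L, two-sided alpha 0.05, 80% power and 80 patients.

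n per arm = 2 × (1.960 + 0.842)² × 3.2² / 2.0² = 40.2, rounded up to 41, or 82 in total. At 40 per arm the power is 79.8%. The stated figure reproduces closely. It concerns lactate and says nothing about the analysis set for clinical outcomes. If 4 of 80 patients were undosed, power for lactate would be 77.8%; if 10 were, 74.4%.

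**Bias in survival when undosed patients are dropped from one arm.** From the documents: 80 patients randomised 1:1, so n = 40 per arm. Assumed, because the documents give no values: true survival s, equal in both arms; k undosed patients, all in the NMB arm; survival q among those k.

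- Observed NMB survival = (n·s − k·q) / (n − k)
- Shift from the truth = k(s − q) / (n − k)

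The sign of the shift is the sign of s − q, so the direction depends entirely on who is left undosed.

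With s = 0.40 and q = 0.10:

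| k | Observed NMB survival | Shift (points) |
|---|---|---|
| 2 | (16 − 0.2)/38 = 41.6% | +1.6 |
| 3 | (16 − 0.3)/37 = 42.4% | +2.4 |
| 4 | (16 − 0.4)/36 = 43.3% | +3.3 |

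**Range over other assumptions** (s from 0.30 to 0.50, k from 1 to 4):

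- All undosed patients died (q = 0): from 1 × 0.30/39 = +0.8 points to 4 × 0.50/36 = +5.6 points, odds ratios 1.04 to 1.25.
- All undosed patients survived (q = 1): from 1 × (0.50 − 1)/39 = −1.3 points to 4 × (0.30 − 1)/36 = −7.8 points.
- No one undosed, or exclusions balanced between arms and unrelated to outcome: no bias.

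**Against sampling error.** With 40 per arm and 40% survival, the standard error of the difference is √(2 × 0.4 × 0.6/40) = 11.0 points, and the 95% interval is about ±21.5 points. A shift of 1.6 to 3.3 points is about 0.14 to 0.30 of a standard error.

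**The case against.** Much can be said for the plan.

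- **Design features limit the problem.** Patients not expected to survive 24 hours were excluded before randomisation, which shrinks the group likely to die or be held back before dosing. The saline marker gives both arms a dosing event and is there to keep the delay from randomisation similar. The modified ITT rule reads the same for both arms. All this stands and makes large imbalance less likely. None of it ensures that losses in that interval are equal. Stratifying by shock balances instability at entry, not what follows.
- **Patient flow will be shown.** A CONSORT diagram is planned. Its shell is missing from the supplied text, so one cannot say that it omits undosed counts or reasons. Even so, a flow diagram does not change the estimate.
- **Some outcomes may be out of reach.** The documents report consent by representatives but are silent on withdrawal. If withdrawal is why a patient went undosed, outcome data may not be usable. This stands, and the fix allows for it.
- **The effect is small and secondary.** The illustrated shift is minor beside a standard error of 11 points, and the trial is sized for lactate. This also stands. It limits the priority but does not justify the exclusion.

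A reader might go further and infer that survival under NMB will be overstated. The documents do not support that: they give neither the number undosed nor their outcomes, and the bias can run either way. Nor do they say that every analysis is restricted. The wording covers initial analyses, although no later, wider one is specified. A reader might also think the primary result is compromised, but the outcome's definition makes modified ITT reasonable there.

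**Conclusion.** The point holds for outcomes that need no dosing event. As written, the rule permits exclusions after randomisation that depend on the arm, and no specified analysis would reveal or correct them.

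The size and direction are unknown. The shift of +1.6 to +3.3 points in NMB survival rests on assumed values (2 to 4 undosed, all in the NMB arm, 10% survival among them, 40% overall); only the 80 patients and 1:1 allocation come from the documents. Across the wider assumptions shown it runs from −7.8 to +5.6 points, and it may be zero. The absence of blinding is judged from the supplied text, from which title and contact pages were removed.

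This is a change worth making, because clinical outcomes form part of the stated hypothesis and the remedy is cheap. It does not put the lactate analysis in doubt.

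**What to change.** Amend General Principles in both documents to say:

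- Survival to discharge, neurologic outcome at discharge, ICU and hospital length of stay, shock-free days and ventilator-free days will be analysed in all randomised patients by assigned arm, except where consent to use data was withdrawn. The modified ITT result for these outcomes will be a sensitivity analysis.
- Lactate and biomarker analyses stay in the modified ITT set.
- Randomised patients who received no study drug will be reported by arm, with the reason and vital status, alongside the planned CONSORT diagram.

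The cost is a wording change and a little record retrieval for any undosed patients. The drawback is slight dilution of a true effect by untreated patients, and the modified ITT sensitivity analysis lets a reader judge it. If no patient went undosed, the two sets coincide and one sentence in the report settles the matter.

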## Outcomes and Definitions

### *Primary Outcome and Sample Size Estimation*

The primary outcome of the study is change in serum lactate level measured between 0-hours and 24-hours after the receipt of study drug. This outcome was chosen as lactate is a continuous variable which is highly correlated with hospital survival in cardiac arrest patients. The 24-hour time point was selected as it was drawn after completion of the rocuronium infusion but not so late that a significant proportion of patients may have already died. Based on conservative estimates drawn from observational data, a sample size of 80 patients was specified to detect a predicted mean difference in 24-hour lactate of 2.0mmol/L ( $\pm 3.2$ mmol/L) with 80% power assuming a two-sided test and an alpha of 0.05.

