### *Analysis of Primary Outcome*

The primary outcome is lactate change between 0-hours and 24-hours after enrollment. The group difference in change from the time of study drug administration (0-hours) to 24-hours will be assessed using a linear mixed effects model. Lactate values will be log-transformed for this analysis if they are not approximately normally distributed. Fixed effects will include the allocated treatment, shock stratification, time point (0-hour, 12-hour, and 24-hour), and the interaction between treatment and time point. Study site will be included as a random intercept. The usual care group will be the reference variable for group, and baseline (0-hour) will be the

reference variable for time. Means and 95% confidence intervals of lactate over time will be presented, by treatment, using longitudinal plots (see appendix Figure 2)

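### The per-protocol rule for usual care has a start but no end, so read literally it drops patients first paralysed after the 24-hour lactate sample

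*SAP*

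**What the plan says.** The wording is the same in the Protocol and the SAP.

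- **Main population** (General Principles): modified intention-to-treat, "defined as all randomly assigned subjects who received any study drug (rocuronium or the saline time marker"). It has no survival or adherence condition.
- **Repeat analysis** (General Principles): "The primary analysis for the outcome of lactate at 24-hours will be repeated in the per-protocol population", a set "including only those patients who were alive at 24-hours".
- **Adherence, NMB arm:** the patient "received either 24-hours of continuous rocuronium (if so assigned").
- **Adherence, usual-care arm:** the comparison is with "those who received usual care without any neuromuscular blockade medication after the time 0-hour point".
- **Endpoint** (Primary Outcome and Sample Size Estimation): "change in serum lactate level measured between 0-hours and 24-hours after the receipt of study drug".
- **Model** (Analysis of Primary Outcome): a linear mixed model with treatment, shock stratum, "time point (0-hour, 12-hour, and 24-hour), and the interaction between treatment and time point" as fixed effects. Study site is the only random effect named.
- **Paralytic reporting** (Appendix Table 2): bolus and continuous rocuronium and cisatracurium are tabulated for both arms at 0, 12, 24 and 36 hours.

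**The concern.** The two arms are judged over different periods. The NMB condition is complete at 24 hours, when the endpoint is measured. The usual-care condition starts at 0 hours and never closes, and a single dose is enough to exclude.

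A blocker first given after the 24-hour sample cannot have influenced that sample. Excluding the patient for it therefore says nothing about adherence during the period under study. It selects on later clinical course, and in one arm only. If patients who need late paralysis had a different lactate course over the first day, the usual-care mean moves for a reason unrelated to treatment received.

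There is a practical side too. One analyst could stop at 24 hours, a second at 36 hours because Appendix Table 2 ends there, and a third at hospital discharge. All three could claim to have followed the plan.

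**Working it through.** **The plan's own figure.** The sample size is not in dispute. With a difference of 2.0 mmol/L, SD 3.2 mmol/L, two-sided alpha 0.05 and 80% power, n per arm = 2 × (1.96 + 0.8416)² × 3.2² / 2.0² = 40.19, rounded up to 41, or 82 in total against the stated 80. With 40 per arm the power is 79.8%. The figure reproduces and the point below does not touch it.

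**Windows side by side.**

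| Item | Starts | Ends |
|---|---|---|
| Primary endpoint | 0 h | 24 h |
| NMB adherence condition | 0 h | 24 h |
| Usual-care adherence condition | 0 h | not stated |
| Paralytic table shell | 0 h | 36 h |

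**Who changes status.** Take a usual-care patient alive at 24 hours.

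| First blocker after 0 h | As written | Window closed at 24-h sample |
|---|---|---|
| None | in | in |
| Before the 24-h sample | out | out |
| After the 24-h sample | out | in |

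Only the last row differs, so the defect is confined to those patients.

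**Size.** If a fraction q of the usual-care patients is removed, and their mean lactate change differs by d from that of the patients left, the usual-care mean shifts by q × d. Here q must be the fraction first paralysed after the sample, and the documents give neither q nor d. A per-patient scale is possible under an assumption. The 80 patients at 1:1 give 40 in usual care, so one patient wrongly removed shifts the mean by d/40. With d assumed to be 0.5 to 1.0 mmol/L, this is 0.5/40 = 0.0125 to 1.0/40 = 0.025 mmol/L per patient. It is slightly more if other exclusions have already reduced the 40. The direction is unknown.

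**The survival condition.** Twenty-four hours of infusion already implies survival to 24 hours, so the separate condition bites mainly on adherent usual-care patients who die. They have no 24-hour lactate in either population. What the per-protocol set loses is their 0-hour and any 12-hour values. With no patient-level random effect named, the model's 0-to-24-hour contrast is essentially a difference between group means at each time. Retained early deaths would enter the 0-hour mean but not the 24-hour mean.

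For illustration, assume no treatment effect, the same change in everyone, deaths in 10% of usual care only, and a baseline 2 to 4 mmol/L higher in those who die. Keeping them raises the usual-care 0-hour mean by 0.10 × 2 = 0.2 to 0.10 × 4 = 0.4 mmol/L and creates a false difference in change of that size. Restricting to 24-hour survivors gives about 0 under the same assumptions.

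**The case against.** The strongest reply is that the sentence is built around 24 hours throughout: the outcome, the survival condition and the infusion. The 0-hour reference is needed because Trial Participants allows an earlier single dose that has worn off. On that reading the window is obviously 0 to 24 hours. This may well be what was meant, and it stands as a reason not to claim that the authors intended a post-outcome exclusion. It does not supply the missing end time, and no other section does.

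A reader might take the 36-hour column under "Paralytic (% receiving") in Appendix Table 2 as proof that late use governs membership. It is not. The table is descriptive, covers sedatives as well, and matches the lactate schedule, in which 36 hours is a secondary time point. It shows only that the plan intends to report use after 24 hours.

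A reader might also infer that the requirement to be alive at 24 hours should go, because it makes the set differ from the main analysis by more than adherence. The difference is real, but removing the condition is a trade-off: under the stated model, keeping early deaths can itself bias the change contrast. The plan also limits such deaths, by excluding patients not expected to survive 24 hours and by choosing a time point before many deaths were expected. What remains is a need to label and count.

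Finally, the two arms are selected on different things in any per-protocol comparison of an infusion with usual care. That is true, and the fix does not remove it.

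**Conclusion.** The point holds as an unclosed window: followed as written, the rule excludes usual-care patients for events after the outcome. It is a minor point, because it touches one supportive repeat analysis.

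No overall size can be given. A tempting calculation assumes that 10 to 30% of usual-care patients are excluded and differ by 0.5 to 1.0 mmol/L, giving 0.1 × 0.5 = 0.05 to 0.3 × 1.0 = 0.30 mmol/L, or up to 15% of the 2.0 target. The documents do not support this as the size of the defect. Both inputs are assumed, and the fraction covers every excluded usual-care patient, most of whom could still be excluded once the window is closed.

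Nor is the per-protocol repeat the plan's only view of off-protocol paralysis, since use is also tabulated by arm and time. It is the only planned re-analysis that addresses it, which is why its membership rule should be unambiguous.

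**What to change.** In General Principles of both documents, change the usual-care condition to: *no neuromuscular blocker between 0 h and the 24-h lactate sample*. Keep the alive-at-24-hours condition and label the analysis as one in 24-hour survivors.

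Report the number excluded by arm and reason, with deaths before 24 hours counted separately from non-adherence. A patient who dies during an otherwise adherent infusion then appears as a death and not as a protocol departure.

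The cost is a few words in each document and a short table, with no new visits or samples. Dose times must be known well enough to place first use before or after the 24-hour sample. The documents do not say whether paralytic use is recorded more finely than the Appendix Table 2 time points, so the plan should state how use at the 24-hour column is classified. Some selection remains, as in any per-protocol set.
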